# 5.6 Study Completion Visit

The study completion visit will occur on Day 181 and will be a clinic visit. In the exceptional situation in which a clinic visit is not possible, such as in the case when a site is not able to see study subjects at the clinic due to local regulations related to the coronavirus pandemic, a home visit may be considered. The date of study completion is the date of the last contact (clinic visit or telephone call) in which the subject's health status was assessed or, in cases where the subject does not agree to any further safety follow-up, it is the date consent is withdrawn. This date should be recorded at the end of Study eCRF page. For visit procedures to be performed for a subject whose planned study participation ends prematurely, please see Section 5.6.1, Early Termination Visit.

During the study completion clinic visit, the subject will be interviewed to determine if any SAEs, AESIs or MAAEs occurred and if any associated concomitant medications or vaccines were taken/received in the time since the last safety assessment. The qualified healthcare professional reviewing these data will discuss the symptoms (if any) reported by the subject and will determine if any additional diagnoses and/or AEs s are present. Adverse events reported by the subject at this follow-up clinic visit must be recorded in the subject's source document and on an Adverse Events eCRF, as specified in Section 7.1, Safety Assessments.

If applicable, a qualified healthcare professional will perform a targeted physical examination based on specific complaints indicated by the subject.

During the visit, approximately 10 mL of blood will be drawn from all subjects (see Section 3.7, Collection of Clinical Specimens).

The site will review with the subject the plan of when information relating to the subject's participation in the study may be available (e.g., study results, treatment assignments). It will also be discussed how information relating to the subject's participation in the study will be shared with the subject's healthcare provider if the subject chooses to share this information.

The site will complete the end of Study eCRF page and this will mark the completion of the subject's participation in the study.

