#### 7.1.2 Unsolicited Adverse Events

An unsolicited AE is an AE that was not solicited using a Subject eDiary and that was spontaneously communicated by a subject who was vaccinated with one of the study vaccines.

Potential unsolicited AEs may be medically attended (defined as symptoms or illnesses requiring hospitalization, or emergency room visit, or visit to/by a qualified healthcare professional), or were of concern to the subject. In case of such events, subjects will be instructed to contact the site as soon as possible to report the event(s). The detailed information about the reported unsolicited AEs will be collected by the qualified site personnel during the interview and will be documented in the subject's records.

The period of observation for AEs extends from the time the subject has received the study vaccine until the subject either completes the specified safety follow-up period (Day 181) or at early study termination.

All unsolicited AEs that start during the treatment period (Day 1 to Day 29) will be recorded in the eCRF. During the follow-up (Day 30 to Day 181), unsolicited AEs that meet any reporting criterion (an SAE, AESI, AE leading to withdrawal or a MAAE) are to be recorded in the eCRF.

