#### 8.4.3.1.3 Analysis of Unsolicited Adverse Events

This analysis applies to all AEs occurring during the study, judged either as probably related, possibly related, or not related to vaccination by the investigator, recorded in the AE eCRF, with a start date on or after the date of vaccination. The original verbatim terms used by

investigators to identify adverse events in the eCRFs will be mapped to preferred terms using the MedDRA dictionary.

The adverse events will then be grouped by MedDRA preferred terms into frequency tables according to system organ class. All reported AEs, as well as AEs judged by the investigator as at least possibly related to study vaccine, will be summarized according to system organ class and the preferred term within system organ class. These summaries will be presented by the vaccination group and by the interval of study observation (Day 1 to Day 29, Day 30 to end of study). When an AE occurs more than once for a subject, the maximal severity and strongest relationship to the vaccine group will be counted.

Separate summaries will be produced for the following categories

- AEs
- SAEs
- AEs that are possibly or probably related to the vaccine
- SAEs that are possibly or probably related to the vaccine
- AESIs
- MAAEs
- AEs leading to withdrawal

Data listings of all adverse events will be provided by subject.

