#### 13.4 Unsolicited Adverse Events

This analysis applies to all AE's occurring during the study, judged either as probably related, possibly related, or not related to vaccination by the investigator, recorded in the AE eCRF.

The original verbatim terms used by investigators to identify adverse events in the eCRFs will be mapped to preferred terms using the MedDRA dictionary.

The adverse events will then be grouped by MedDRA preferred terms into frequency tables according to system organ class. All reported AEs, as well as AEs judged by the investigator as at least possibly related to study vaccine, will be summarized according to system organ class and the preferred term within system organ class. These summaries will be presented by vaccination group. When an AE occurs more than once for a subject, the maximum severity and strongest relationship to the vaccine group will be counted.

The assignment to safety follow-up time intervals will be done by day of onset and not by days ongoing/persisting.

26 Augustus 2021 Final Version 2.0

The summaries will be presented by period of onset (Day 1 to Day 29, Day 30 to end of study or Day 1 to end of study). An overview summary will be created by time -period with number and % of subjects with the following categories:

- AE
- AE by maximum severity
- Related (i.e. at least possible) AE
- SAEs
- Related SAEs
- AESIs
- MAAEs
- AEs leading to withdrawal from study
- Deaths.

The following summaries will be produced by SOC and Preferred Term and by time-period (Day 1 to Day 29, Day 30 to end of study or Day 1 to end of study):

- AEs
- AEs by maximum severity
- AEs that are possibly or probably related to the vaccine
- SAEs
- SAEs that are possibly or probably related to the vaccine
- AESIs
- MAAEs
- AEs leading to withdrawal
- Deaths.

Data listings of all adverse events will be provided by subject. In addition, adverse events in the categories above will be provided as listed data.

All tables will be produced overall and by age subgroup.

Print Date (Local): 26-Aug-2021 16:31:00

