# 13.5 Combined Solicited and Unsolicited Adverse Events

A summary of subjects with all combined solicited (regardless of their duration) and unsolicited adverse events will be provided. Solicited adverse events will be coded by MedDRA. For clinicaltrials.gov posting purposes, a summary of combined solicited and unsolicited non-serious adverse events will be produced by System Organ Class and according to occurrence of each event based on the Overall Safety set.

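### SAP 13.4 tabulates all AEs, AE severity and related AEs beyond Day 29, although only SAEs, MAAEs, AESIs and withdrawal AEs are collected from Day 30, so those rows under-count and the pooled row has no clear meaning

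*SAP*

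**What the plan says.** **Collection.** Under Protocol 7.1.2, every unsolicited AE with onset on Day 1–29 goes into the eCRF. For Day 30 to Day 181 the rule narrows: "unsolicited AEs that meet any reporting criterion (an SAE, AESI, AE leading to withdrawal or a MAAE) are to be recorded in the eCRF". SAP 3.1 repeats this. The Day 91 call script (Protocol 5.4.2) asks only for those four categories, and the event schedules in both documents have no assessment of general unsolicited AEs at Day 91 or Day 181.

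**Tables.** SAP 13.4 opens with "This analysis applies to all AE's occurring during the study", as recorded in the AE eCRF. On periods it says: "The summaries will be presented by period of onset (Day 1 to Day 29, Day 30 to end of study or Day 1 to end", the last one covering the whole study. An overview table covers any AE, AE by maximum severity, related AE, SAEs, related SAEs, AESIs, MAAEs, withdrawal AEs and deaths. Then: "The following summaries will be produced by SOC and Preferred Term and by time-period", with the same categories. Nothing restricts, retitles or footnotes the first three for the later periods.

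**Protocol intervals.** Protocol 8.4.3.1.3 presents the summaries "by the interval of study observation (Day 1 to Day 29, Day 30 to end of study"). It has no pooled Day 1-to-end interval. SAP 13.4 adds one, and SAP 16 does not list it as a change.

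**Endpoints.** All unsolicited AEs are a primary safety endpoint to Day 29 (Protocol 8.1.1.2). To end of study, the secondary endpoint names only the four restricted categories among unsolicited events (Protocol 8.1.2.2).

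**Registry summary.** In SAP 13.5, "a summary of combined solicited and unsolicited non-serious adverse events will be produced by System Organ Class", for public posting. No time window is given for its unsolicited part.

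**The concern.** A row labelled as any AE tells the reader that all AEs in the period were sought. After Day 29 that is untrue: an AE that is not serious, not medically attended, not of special interest and did not lead to withdrawal is not collected. The row for Day 30 to end of study is really a row for four reportable categories under a broader name. The row for Day 1 to end of study changes its case definition part-way through.

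At stake is the reading of the 180-day safety tables in the study report and of the posted summary. A reader of the posted summary will not have SAP 3.1 alongside. Someone could take the pooled percentage as the 180-day AE incidence, or set it against the Day 1–29 percentage as if the two measured the same thing.

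**Working it through.** The plan states no figure to reproduce here. The check compares the collection rule with the table specification, then illustrates the size.

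**1. Rule against tables**

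| Row in SAP 13.4 | Collected Day 1–29? | Collected Day 30–181? | Endpoint beyond Day 29? |
|---|---|---|---|
| Any AE, by severity, related | Yes, all | Only if SAE, MAAE, AESI or withdrawal AE | None |
| SAE, related SAE, MAAE, AESI, withdrawal AE, death | Yes | Yes | Yes (Protocol 8.1.2.2; deaths are SAEs) |

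Only the first line has a mismatch.

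**2. Days under each rule.** Full collection: Day 1–29, 29 days. Restricted collection: Day 30–181, 181 − 30 + 1 = 152 days. Shares: 29/181 = 16.0% and 152/181 = 84.0%.

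**3. Direction.** Leaving out non-qualifying events can only lower, never raise, the percentage of subjects with at least one AE or at least one related AE. This part follows from the rule alone.

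**4. Size, under assumptions not in the documents.** Let p be the percentage of subjects with an AE on Day 1–29, with constant hazard h = −ln(1 − p)/29 per day. Let q be the share of AEs that meet a reporting criterion. Then:

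- Day 30–181, full: 1 − exp(−152h); recorded: 1 − exp(−152qh)
- Day 1–181, full: 1 − exp(−181h); recorded: 1 − exp(−(29 + 152q)h)

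Example: p = 0.20 gives h = 0.2231/29 = 0.00769. With q = 0.2 the effective exposure is 29 + 30.4 = 59.4 days, so 1 − exp(−0.457) = 36.7% is recorded, against 1 − exp(−1.393) = 75.2%.

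| p | q | Day 30–181 full | Day 30–181 recorded | Day 1–181 full | Day 1–181 recorded |
|---|---|---|---|---|---|
| 15% | 0.3 | 57.3% | 22.6% | 63.7% | 34.2% |
| 15% | 0.6 | 57.3% | 40.0% | 63.7% | 49.0% |
| 20% | 0.2 | 69.0% | 20.9% | 75.2% | 36.7% |
| 20% | 0.3 | 69.0% | 29.6% | 75.2% | 43.7% |
| 20% | 0.5 | 69.0% | 44.3% | 75.2% | 55.4% |
| 30% | 0.3 | 84.6% | 42.9% | 89.2% | 60.0% |
| 30% | 0.6 | 84.6% | 67.4% | 89.2% | 77.2% |

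The shortfall in the pooled row runs from 89.2 − 77.2 = 12.0 to 75.2 − 36.7 = 38.5 percentage points.

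**5. Mix of severity and relatedness.** Take an assumed true mix of 60/32/8% mild/moderate/severe. If 20/50/90% of each grade qualify, the recorded mix is 0.120/0.160/0.072 divided by 0.352, or 34/45/20%. With 40/60/90% qualifying it is 48/38/14%. With equal capture it stays 60/32/8%. For relatedness, take a true related share of 20%. If 20% of related and 50% of unrelated AEs qualify, it becomes 0.04/0.44 = 9%; with equal capture it stays at 20%. So the mix moves only if qualifying depends on grade or relatedness. That is plausible for severity, but the documents fix neither the size nor, for relatedness, the direction.

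**The case against.** The best defence is that this is only a labelling matter. SAP 3.1 states the collection rule, and SAP 13.4 limits itself to AEs in the AE eCRF. A separate Day 1–29 table gives the clean 28-day figure, the safety analysis is descriptive, and the same filter applies to all eight arms. The MAAE category is also broad (any AE leading to a visit to a healthcare provider, Protocol 7.1.3), so many mild events are still captured after Day 29. All of this stands, and it limits the harm. It does not give the pooled row a meaning, and the tables themselves do not disclose the filter.

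It can also be said that deleting rows removes safety data from view. It need not: every qualifying later event appears in its own category table, and SAP 13.4 lists all AEs by subject. Retitling is nevertheless an acceptable alternative.

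A reader might infer more than the documents support:

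- *AEs will appear to fall sharply after Day 29.* The overview gives percentages of subjects per period, and the second period is about five times as long (152/29 = 5.2). In the table above, the recorded Day 30–181 figure is 20.9–44.3% against 20% before, so it is level or higher. The fall to q times the earlier value is in a daily rate that SAP 13.4 does not plan to show.
- *Severity and relatedness shift by construction.* Only the under-count does (steps 3 and 5).
- *Formulation choice is distorted.* Protocol 8.6 says the Day 29 read-out is the one meant to inform Phase 3, and within a period the arms are compared like for like.
- *Protocol 5.6 invites other AEs at Day 181*, because it says "Adverse events reported by the subject at this follow-up clinic visit must be recorded in the subject's source document and on an Adverse Events eCRF". The sentence goes on to refer to Section 7.1, which contains the restriction, and the Day 181 interview is directed at SAEs, AESIs and MAAEs.

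**Conclusion.** The point holds as a mismatch between three table types and the collection rule. That the later-period rows for any AE and related AE under-count is certain from the documents. So is the mixed definition of the pooled row (29 days full, 152 days filtered), which makes it not comparable with the Day 1–29 row. The size is not known. The 12 to 39 point shortfall rests on a constant hazard, 15–30% incidence by Day 29 and 20–60% of AEs qualifying, none of which the documents give. A change in severity mix is possible but unquantified.

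The Day 1–29 safety endpoint, the rows for SAEs, MAAEs, AESIs, withdrawal AEs and deaths, between-arm comparison within a period, and the immunogenicity analysis are untouched. The change should be made because no stated endpoint needs the affected rows and the correction is cheap.

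**What to change.** 1. In SAP 13.4 and Protocol 8.4.3.1.3, limit the all-AE, maximum-severity and related-AE tables (overview and SOC/PT, overall and by age subgroup) to onset on Day 1–29. This matches Protocol 8.1.1.2.
2. For Day 30 to end of study and Day 1 to end of study, present only SAEs, related SAEs, MAAEs, AESIs, AEs leading to withdrawal and deaths. This matches Protocol 8.1.2.2.
3. If any broader row is kept for those periods, retitle it as SAE, MAAE, AESI or AE leading to withdrawal. In the pooled row, apply that filter to Day 1–29 events too; a new title alone would leave the two definitions mixed.
4. In SAP 13.5, state the collection window for the unsolicited part of the combined summary: all AEs with onset to Day 29, and only the reportable categories after that.

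The cost is revised wording and table shells, with fewer tables and no new data. The downside is that there is no single all-AE figure for the whole study; the collection rule could not have supported one.

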# 13.5 Combined Solicited and Unsolicited Adverse Events

A summary of subjects with all combined solicited (regardless of their duration) and unsolicited adverse events will be provided. Solicited adverse events will be coded by MedDRA. For clinicaltrials.gov posting purposes, a summary of combined solicited and unsolicited non-serious adverse events will be produced by System Organ Class and according to occurrence of each event based on the Overall Safety set.

# **13.6 Clinical Safety Laboratory Investigations**

Not applicable.

# 13.7 Concomitant Medication

Medications and vaccines taken prior or during the study are categorized as pre-trial and/or concomitant. In addition, a subset of concomitant medications is defined for the period Day 1 to 29 (see section 8.7 for definition).

Medications (generic drug name) will be coded using the WHODRUG dictionary.

The frequencies and percentages of subjects reporting pre-trial, concomitant medications (Day 1 -29 and Day 1 to end of study) will be tabulated by vaccine group.

# **14. INTERIM ANALYSIS**

There are no planned interim analyses for this study. The statistical analyses will be performed stepwise in two parts, as follows:

1. A final analysis including all immunogenicity and safety data collected from Visit 1 to Visit 3 (Day 29) and associated primary and secondary objectives will be conducted on cleaned and locked data. No individual listings and unblinding data will be generated at this stage. Access to information about study groups will be limited by a biostatistician in charge of statistical analysis.

2. The analysis of immunogenicity and safety data collected between Visit 3 and Visit 5 will be performed after all data is available. The results of this analysis will cover the entire study duration. All results will be presented in the clinical study report and will include individual data listings and unblinded information.

# **15. DATA MONITORING COMMITTEES**

An internal safety team (IST) – independent of the study team - will be installed to monitor the safety data collected during the enrollment of the subjects in the study. Details are included in the IST charter. In addition, upon request an independent DMC will be asked to review the safety data and make recommendations for the conduct of the trial. Further details are described in the DMC charter.

# Alerting and pausing rules

A summary table will be created with number and % of subjects who met one of the criteria by treatment based on the solicited or unsolicited Safety set.

- Any SAE that cannot be reasonably attributed to a cause other than vaccination, according to the Investigator's assessment, within 7 days post-vaccination (i.e. probable).
- Severe systemic hypersensitivity such as anaphylaxis, within 24 hours after study vaccination.
- Any Grade 3 (severe) local solicited AE lasting ≥2 consecutive days, within 7 days postvaccination.
- Any Grade 3 (severe) systemic solicited AE lasting ≥2 consecutive days, within 7 days postvaccination.
- Any severe unsolicited AE that cannot be reasonably attributed to a cause other than vaccination (i.e. probable), within 7 days postvaccination.

# **16. CHANGES TO PLANNED ANALYSIS**

Compared to the final protocol, an additional safety set may be defined for the investigator assessment of the solicited adverse events. This will only be applicable if there are subjects without any eDiary data, but with an investigator assessment of the solicited adverse events.

The SAP, version 1.0, 16 April 2021 has been amended with a few changes mainly related to the programming of data sets.

- The window around the Day 29 sample visit has been extended to -7 and + 21 days with respect to the Day 29 visit to be included in the PP analysis.
- The Day 181 FAS and PPS have been defined in more detail
- Last vaccination prior to study will be categorized as 1 year before, 2 years or 3 years before
- The investigator assessment will be derived both on the overall consistency as well as the particular symptom.

# **17. LIST OF FINAL REPORT TABLES, LISTINGS AND FIGURES**

The list of tables, listings and figures will be developed based on the final version 1.0 of this statistical analysis plan. This will be documented as part of the TLF shells. Numbering will follow ICH E3 guideline on clinical study report.

